8.2.4 Final Analysis of Efficacy

Efficacy analysis will be conducted using the Efficacy Population. The primary outcome (ORR per RECIST) will be presented together with a 95% CI for each treatment arm. Treatment arms with an observed ORR 95% CI with a lower limit above 20% and an upper limit above 40% will be considered for future study. All other outcomes measures will be summarized with the appropriate descriptive statistics.

Additional detail regarding derivation and analysis of efficacy outcomes are provided below:

- ORR per RECIST is defined as the proportion of patients whose best overall response is CR or PR;
- ORR per iRECIST is defined as the proportion of patients whose best overall response is immune CR (iCR) or immune PR (iPR);
- Duration of response (DOR) per RECIST will be calculated for patients with CR or PR as the best overall response. DOR is defined as the number of weeks from the start of the first response (CR or PR) to the first date of progressive disease per RECIST, clinical progression, or death due to any cause. DOR will be summarized descriptively using the Kaplan-Meier method;
- Immune DOR (iDOR) per iRECIST will be calculated for patients with iCR or iPR as the best overall response. iDOR is defined as the number of weeks from the start of the first response (iCR or iPR) to the first date of progressive disease per iRECIST, clinical progression, or death due to any cause. iDOR will be summarized descriptively using the Kaplan-Meier method;
- Disease control rate (DCR) per RECIST is defined as the proportion of patients whose best overall response is CR, PR, or SD; (DCR = CR + PR + SD). DCR will be summarized descriptively;
- Immune DCR (iDCR) per iRECIST defined as the proportion of patients whose best overall response is iCR or iPR or immune SD (iSD) per iRECIST; (iDCR = iCR + iPR + iSD). iDCR will be summarized descriptively;
- PFS is defined as the time from the initiation of study treatment to the first occurrence of disease progression per RECIST or death from any cause, whichever occurs first. PFS will be summarized descriptively using the Kaplan-Meier method;
- Immune PFS (iPFS) is defined as the time from the initiation of study treatment to the first occurrence of disease progression per iRECIST or death from any cause, whichever occurs first. iPFS will be summarized descriptively using the Kaplan-Meier method;
- OS is defined as the time from the initiation of study treatment to death from any cause and will be summarized descriptively using the Kaplan-Meier method;
- Time to response (TTR) per RECIST will be calculated for patients with CR or PR as the best overall response. TTR is defined as the time from first dose date to the start of the response (CR or PR) per RECIST. TTR will be summarized descriptively using the KaplanMeier method; and
- Immune TTR (iTTR) per iRECIST will be calculated for patients with iCR or iPR as the best overall response. iTTR is defined as the time from first dose date to the start of the first response (iCR or iPR) per iRECIST. iTTR will be summarized descriptively using the Kaplan-Meier method.

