The sample size calculation is based on a Simon's 2-stage⁴⁰ design and ensures that under all possible distributions of patients to the 2 treatment arms, there is at least 80% power to correctly detect an ORR >40% and at most a Type I error rate of 10% of rejecting a null hypothesis that ORR <20%. This results in a sample size of 12 patients randomized to each treatment arm in Stage 1, followed by 13 additional patients randomized during Stage 2: a total of 25 patients per arm at the end of Stage 2.

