### 3.4.3 Primary Efficacy Endpoints

For Part 1 (Monotherapy Dose expansion) and Part 3 (Combination Dose Expansion), the primary efficacy endpoint is ORR using RECIST 1.1

The point estimates of ORR along with the exact Clopper-Pearson 95% CI will be presented by treatment arm in the Monotherapy Dose Expansion part and Combination Dose Expansion part and overall based on the Efficacy Population.

For Part 2 (Combination Dose Finding), the efficacy analyses are considered as secondary (see Section 3.4.4).

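### Part 3's only final criterion (95% CI lower limit above 20%) needs 10 of 25 responses, giving 57% power at an ORR of 40%, not the stated 80%

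*Protocol*

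**What the plan says.** Protocol 8.2.1 (Combination Dose Expansion part) sizes each arm by Simon's two-stage method. It promises "at least 80% power to correctly detect an ORR >40"%. For error control it allows "at most a Type I error rate of 10% of rejecting a null hypothesis that ORR <20"%. Stage 1 has 12 patients per arm and Stage 2 adds 13, which makes 25. The synopsis and SAP 2.2.4 repeat this.

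The Stage 1 boundary is given in Protocol 3.1.3 (Table 8), Protocol 8.2.3 and SAP section 4: an arm stops with 2 or fewer responses in 12 and continues with 3 or more.

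No final Simon boundary, meaning a number of responses out of 25, appears in either document. The only end-of-Part-3 criterion is in Protocol 8.2.4 and the synopsis, where arms with "an observed ORR 95% CI with a lower limit above 20% and an upper limit above 40% will be considered for future study". The protocol does not name the interval method. SAP 3.4.3 does: "The point estimates of ORR along with the exact Clopper-Pearson 95% CI will be presented by treatment arm". The SAP does not carry the protocol's CI criterion and does not replace it with another.

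**The concern.** A Simon design's power and type I error belong to a specific pair of boundaries, one at Stage 1 and one at the end. Sizing the arm for one final boundary and then judging it by another leaves the stated properties without a basis. A two-sided 95% interval with its lower limit above 20% works as a one-sided test at no more than 2.5%, while the sample size was set for 10%. The written rule must therefore be stricter than the design it is attached to.

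What is at stake is the go/no-go decision on the primary endpoint. With 8 or 9 responses of 25, the design behind the sample size rejects the null, while the written criterion does not put the arm forward. Two readers of the same protocol would reach opposite conclusions.

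**Working it through.** **Inputs.** Null ORR 20%, target ORR 40%, type I error at most 10%, power at least 80%, n1 = 12, n = 25 (Protocol 8.2.1). Stop if 2 or fewer of 12 respond (Protocol 3.1.3, 8.2.3). Final criterion: 95% CI lower limit above 20% and upper limit above 40% (Protocol 8.2.4). Interval: exact Clopper-Pearson (SAP 3.4.3). All 25 patients are assumed to be in the Efficacy Population.

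**Formula.** For a final boundary of R or more responses of 25,

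P(success | p) = Σ over x = 3 to 12 of P(X1 = x; 12, p) × P(X2 ≥ R − x; 13, p).

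**Step 1: reproduce the stated design.** A full search over two-stage designs for 20% versus 40% (type I error ≤ 10%, power ≥ 80%) gives as the optimal design n1 = 12, stop at ≤ 2, n = 25, reject at ≥ 8. Its type I error is 9.91%, its power 81.5%, and its expected sample size under the null 17.7. The protocol's 12 + 13 is therefore correct for R = 8.

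**Step 2: find what the written criterion requires.** Clopper-Pearson 95% limits for x/25:

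| Responses | Lower | Upper | Meets criterion |
|---|---|---|---|
| 8 | 14.9% | 53.5% | no |
| 9 | 18.0% | 57.5% | no |
| 10 | 21.1% | 61.3% | yes |

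So R = 10. The upper-limit clause never binds, because the upper limit is already 61.3% at the first count that meets the lower-limit clause.

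**Step 3: power at p = 0.40 with R = 10.**

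| x in Stage 1 | P(X1 = x) | P(X2 ≥ 10 − x) | Product |
|---|---|---|---|
| 3 | 0.1419 | 0.2288 | 0.0325 |
| 4 | 0.2128 | 0.4256 | 0.0906 |
| 5 | 0.2270 | 0.6470 | 0.1469 |
| 6 | 0.1766 | 0.8314 | 0.1468 |
| 7 | 0.1009 | 0.9421 | 0.0951 |
| 8 | 0.0420 | 0.9874 | 0.0415 |
| 9 | 0.0125 | 0.9987 | 0.0124 |
| 10 to 12 | 0.0028 | 1 | 0.0028 |

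The sum is 0.569. The same sum at p = 0.20 is 0.017.

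**Step 4: compare the two rules.**

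| Final rule after ≥ 3/12 | Type I error at 20% | Power at 40% | at 45% | at 50% |
|---|---|---|---|---|
| ≥ 8/25 (Simon) | 9.9% | 81.5% | 91.4% | 96.5% |
| ≥ 10/25 (written CI criterion) | 1.7% | 56.9% | 75.1% | 88.0% |

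Under the written criterion, power first reaches 80% at a true ORR of about 47% (78.2% at 46%, 81.0% at 47%). The interim look is not the cause: ignoring it, ≥ 10/25 has power 57.5% and type I error 1.7%.

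**Step 5: sensitivity to the interval method.** Wald (9/25 lower limit 17.2%) and Jeffreys (19.5%) also need 10/25. Wilson and Agresti-Coull pass at 9/25 (lower limits just above 20%), giving power 71.0% and type I error 4.5%. Lowering the confidence level does not recover the design either. The 90% and 80% Clopper-Pearson intervals both need 9/25; at 80%, 8/25 has a lower limit of 19.6%. No variant tried reaches 80% power.

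**The case against.** The strongest reply is that the CI sentence is a development filter and not the hypothesis test. It says qualifying arms will be considered for future study; it does not say the null is rejected only then. SAP 3.1.4 also states that no formal hypothesis testing is planned. On that reading the Simon statement in 8.2.1 is correct, and a sponsor may properly set a higher bar for further development than for rejecting 20%. That would be a legitimate choice, but it is not what is written. The power and type I error in 8.2.1 are explicitly those of rejecting a null hypothesis, and no other rejection rule exists in either document. If the CI sentence is not that rule, the 80% and 10% have nothing to attach to. Either reading needs a correction.

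Second, the 57% joins a criterion from the protocol to an interval method from the SAP. That is true, and the size of the shortfall depends on it: 71% under Wilson or Agresti-Coull. The existence of a shortfall does not.

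Third, Part 3 never opened. SAP sections 1 and 5 record that the trial stopped after Part 1 and that all Part 2 and Part 3 analyses were dropped. This stands as a limit on practical consequence: no patient, decision or reported result is touched. It does not correct the figure, which the SAP, finalized after the stop, still repeats.

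**Conclusion.** The concern holds. The sample size is right for a final boundary of 8 or more of 25, but the only final criterion written needs 10 or more of 25. Power at the target ORR is then 56.9% against the stated minimum of 80%, and type I error is 1.7% against the allowed 10%. An arm exactly at 40% would miss the criterion 43% of the time (100 − 56.9), compared with 18.5% (100 − 81.5) under the Simon boundary.

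These figures assume the SAP's Clopper-Pearson interval, the Stage 1 stop applied as written, and 25 evaluable patients per arm. The Efficacy Population requires a post-baseline tumor assessment, so the evaluable number could be lower.

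**What to change.** State the final boundary in Protocol 8.2.4 and the synopsis, and in SAP 2.2.4 and 3.4.3: after at least 3 responses in 12 at Stage 1, reject the null (ORR of 20% or less) if at least 8 of 25 patients respond. Present the 95% Clopper-Pearson interval as descriptive and drop the upper-limit clause, which does nothing.

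If the stricter bar is intended, keep the CI criterion, name the interval method beside it, and restate the properties as 57% power at 40% and 1.7% type I error. If both are wanted, give the Simon boundary as the test and label the CI condition as an additional development criterion with its own operating characteristics. Switching to an 80% exact interval is not a substitute, because 8/25 still fails.

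The cost is wording only, with no extra patients. Because Part 3 was not run, the correction matters for the accuracy of the record and for any later protocol that reuses the design.

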1.3.4 Clinical Experience

In the ANV419-001 (NCT04855929) Phase 1 dose finding study of ANV419, 34 patients with Eastern Cooperative Oncology Group (ECOG) Performance Status 0 or 1 and a range of primary tumor types with multiple previous lines of therapy, including immunotherapy, targeted therapy, and chemotherapy, have been enrolled and treated as of 07 November 2022.

[figure not shown]

Table 1 Study ANV419-001: Grade 3 or Higher Drug Related Treatment-Emergent Adverse Events

System Organ Class	Preferred Term	No Subjects (%) N=34
Blood and lymphatic system disorders	Lymphopenia	3 (9%)
Investigations	ALT increase	1 (3%)
	AST increase	2 (6%)
	Blood bilirubin increase	1 (3%)
	Blood creatinine increase	2 (6%)
	Platelet count decrease	1 (3%)
Gastrointestinal	Nausea	2 (6%)
disorders	Diarrhea	1 (3%)

Skin and subcutaneous	Pemphigoid	1 (3%)
tissue disorders		
Immune system	Cytokine Release Syndrome	1 (3%)
disorders		
General disorders and	Pyrexia	1 (3%)
administration site	Asthenia	1 (3%)
conditions		

[figure not shown]
[figure not shown]

Figure 1. ANV419 Effect on Lymphocyte Count over Treatment Cycles

A comprehensive summary of all drugs related TEAEs reported in the ongoing ANV419-001 study is presented in Appendix F.

Pharmacodynamic Effect

Pharmacodynamic markers of target engagement have been investigated at each dose of ANV419 and up to

Figure 2. ANV419 and Preferential Proliferation of CD8+ and NK Cells

CD = cluster of differentiation; NK = natural killer; Treg = regulatory T cell.

Preliminary Efficacy

Among the 34 patients treated, 33 patients were evaluable for tumor response using RECIST v1.1

Twenty patients (61%) achieved SD or better (19 SD, 1 confirmed PR).

14/20 patients (70%) achieved SD (13 SD, 1 confirmed PR).

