3.1.1 Part 1: Monotherapy Dose Expansion

The Monotherapy Dose Expansion part (Arms A1 and A2) will be a parallel group part with a Bayesian sequential monitoring analysis²⁸ and up to 15 patients per arm. This part will establish the efficacy and safety of ANV419 as monotherapy.

Two doses of ANV419 will be explored: based on data collected in the ongoing Phase 1 ANV419-001 study at a frequency of within the current Protocol in the absence of disease progression or unacceptable toxicity and in the absence of data from Arms A1 and A2 showing an unfavorable risk/benefit profile for patients on ANV419 monotherapy.

Decision making on whether to continue the study beyond the Monotherapy Dose Expansion part, and the total number of patients recruited to this part, will be based on Bayesian sequential monitoring. The study will be stopped at the end of this part in the case of an unfavorable risk/benefit profile for ANV419 monotherapy. This includes observing a total of 0 of 30 responses from the 2 monotherapy arms combined (a strong signal that ANV419 does not induce a response) and/or report of any safety issues that might stop the trial. There is 95% certainty that the true objective response rate (ORR) is greater than 10% if we observe any 1 of the following:

- 2 responses in 3 to 7 patients;
- 3 responses in 8 to 13 patients;
- 4 responses in 14 to 19 patients; or
- 5 responses in 20 to 27 patients.

Response (complete response [CR] or partial response [PR]) will be assessed locally at each disease evaluation.

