recorded at Screening. Target lesions are to be selected on the basis of their size (ie, those with the longest diameter) and suitability for accurate repeated measurement. Lymph nodes may be selected as target lesions; they must be defined as measurable and only the short axis of the node will contribute to the baseline sum. All other pathologic nodes with short axis ≥ 10 mm but <15 mm should be considered nontarget lesions.

• Nontarget: All other lesions not classified as target lesions (or sites of disease) are to be identified as nontarget lesions and are to be recorded in the electronic Case Report Form (eCRF). Measurement of nontarget lesions is not required.

The sum of diameters (longest for non-nodal lesions and short axis for nodal lesions) for all target lesions is to be calculated and recorded in the eCRF as the baseline sum diameters.

Disease response in target and nontarget lesions will be assessed by the Investigator using RECIST 1.1, according to the categories and criteria described in Table 22 below. The best overall response for each patient will be reported as the best response documented over the sequence of objective statuses recorded using the categories and criteria in Table 22.

Table 22. Response Evaluation Criteria in Solid Tumors (RECIST) 1.1 Guidelines for Tumor Response

Tumor response								
Disease Response Criteria for Target and Non-Target Lesions								
Evaluation of target lesions								
	Disappearance of all target lesions. Any pathologic							
	nodes (whether target or nontarget lesions) must have a							
Complete response	reduction in SAD to <10 mm.							
	At least a 30% decrease in the SOD (LD for non-nodal							
	lesions and SAD for nodal lesions) of target lesions,							
Partial response	taking as reference the baseline sum LD.							
·	Neither sufficient shrinkage to qualify for PR nor							
	sufficient increase to qualify for progressive disease,							
	taking as reference the smallest sum LD since the							
Stable disease	treatment started.							
	At least a 20% increase in the SOD of target lesions,							
	taking as reference the smallest sum on study (this							
	includes the baseline sum if that is the smallest sum on							
	study). In addition to the relative increase of 20%, the							
	sum must also demonstrate an absolute increase of at							
	least 5 mm (Note: The appearance of 1 or more new							
Progressive disease	lesions is also considered progression).							

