#### *3.4.1 Best Overall Response (BOR)*

Best Overall Response (BOR) will be determined based on the overall visit responses.

BOR per RECIST v1.1 is defined as the best response in the order of: Complete Response (CR), Partial Response (PR), Stable Disease (SD), Progressive Disease (PD), and Not Evaluable (NE) for patients with measurable disease. The minimum duration of Stable Disease to be considered as the best overall response is 3 weeks from first dose of the study treatment.

iBOR per iRECIST is defined as the best response in the order of: Immune Complete Response (iCR), Immune Partial Response (iPR), Immune Stable Disease (iSD), Immune Confirmed Progression (iCPD), Immune Unconfirmed Progression (iUPD) and NE for patients with measurable disease. The minimum duration of Immune Stable Disease to be considered as the best overall response is 3 weeks from first dose of the study treatment.

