#### *3.4.2 Definition of Efficacy Endpoints*

##### *3.4.2.1 Objective Response Rate (ORR)*

Objective Response Rate per RECIST v1.1 (ORR) is defined as the percentage of patients whose BOR is either CR or PR.

iORR per iRECIST is defined as the percentage of patients whose best overall response is either iCR or iPR.

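### Primary ORR counts an unconfirmed CR or PR from one local reading and compares it with fixed rates, so false responses bias it upward

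*Protocol*

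**What the plan says.** Protocol 8.2.4 defines the primary outcome: "ORR per RECIST is defined as the proportion of patients whose best overall response is CR or PR". SAP 3.4.2.1 says the same: ORR "is defined as the percentage of patients whose BOR is either CR or PR".

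Best overall response is a best-of-visits rule in both documents. Protocol Appendix C: "The best overall response for each patient will be reported as the best response documented over the sequence of objective statuses recorded". SAP 3.4.1: "Best Overall Response (BOR) will be determined based on the overall visit responses". SAP 3.4.1 sets a minimum duration (3 weeks) for SD only. The target-lesion threshold for PR in Appendix C is "At least a 30% decrease in the SOD" from baseline. Confirmation is required only for progression under iRECIST (Appendix D).

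On the reader, Protocol 3.1.1 says: "Response (complete response [CR] or partial response [PR]) will be assessed locally at each disease evaluation". The study is open-label (Protocol 5.3). Images are stored centrally, but central analysis is only a possibility (Protocol synopsis).

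The comparisons are with fixed rates: below 6% is failure and above 10% success in Part 1, and 20% versus 40% applies in Part 3 (Protocol 8.2.1, 8.2.4). The counts that drive decisions are small:
- At least 2 responses in Part 1 are tied to Part 2 (Protocol 3.1.2, SAP 2.2.1.2).
- At least 3 of 12 continue an arm in Part 3. This may be read once 12 patients have had one disease evaluation or have discontinued (Protocol 8.2.3, SAP section 4).

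**The concern.** One reading at or beyond −30% makes a patient a responder for good, even if the next scan does not show it. Taking the best of several scans gives measurement error several chances to cross the threshold. In a comparison between arms this error would fall on both sides. Here each arm is set against a fixed number, so it moves the estimate in one direction only. With counts as small as 2 of 30 or 3 of 12, one or two such readings can change whether the programme moves on. Because Stage 1 can be read after a single evaluation, that decision can rest entirely on single-scan responses.

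**Working it through.** **1. The plan's own figures.** A search for the Simon optimal design (20% versus 40%, type I error at most 10%, power at least 80%) returns 12 patients in Stage 1, stop at 2 or fewer, 25 in total, success at 8 or more. Exact type I error is 9.9% and power 81.5%. The stated 12 + 13 = 25 is reproduced. The Part 1 figures also reproduce under the uniform prior: 0/15 gives 5.9% (0.3%, 17.1%) and 0/30 gives 3.1% (0.2%, 9.2%). The sample size is sound on its own terms; the question is what counts as a response.

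**2. Per-patient false PR.** Assumptions, none from the documents: three on-study scans (the schedule is blacked out), and independent log-normal error with CV s on the baseline sum and on each follow-up sum. Let d be the true change and e0 the baseline error. Given e0, a scan reads as PR with probability p = Φ{[ln(0.70/(1+d)) + e0]/s}. Averaging over e0:
- PR on at least one of three scans: E[1 − (1−p)³]
- PR on two consecutive scans: E[2p² − p³]

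| Assumed CV | True change | At least one scan | Two consecutive |
|---|---|---|---|
| 5% | 0 | about 0% | about 0% |
| 5% | −10% | 0.06% | about 0% |
| 5% | −20% | 7% | 1% |
| 10% | 0 | 1.6% | 0.1% |
| 10% | −10% | 9.2% | 1.3% |
| 10% | −20% | 34% | 10% |
| 15% | 0 | 11% | 2% |
| 15% | −10% | 25% | 6% |
| 15% | −20% | 48% | 18% |

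Confirmation does not remove the error entirely, because all follow-up scans share the same baseline reading.

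**3. Effect on the decision counts.** Let q be the share of true non-responders with a false PR; the documents give no value, so 2%, 5% and 10% are shown. With true ORR t, the apparent rate is t + (1−t)q.

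- *At least 2 responses in 30, t = 0.* For q = 5%: 1 − 0.95³⁰ − 30 × 0.05 × 0.95²⁹ = 1 − 0.2146 − 0.3389 = 0.446. For 2%, 5%, 10%: 12%, 45%, 82%.
- *Same count, t = 6% (the top of the failure range).* 54.5% with no false PRs; then 69.6%, 84.6%, 95.7%.
- *Passing Stage 1 (at least 3 of 12), t = 20%.* Apparent rates are 21.6%, 24% and 28% (for q = 5%: 0.20 + 0.80 × 0.05 = 0.24). The chance rises from 44.2% to 49.8%, 57.8%, 69.6%.
- *Final Part 3 rule, t = 20%.* A Clopper-Pearson lower limit above 20% needs 10 of 25 (lower limit 21.1%; 9 of 25 gives 18.0%). With the Stage 1 stop included, the chance rises from 1.7% to 2.8%, 5.5%, 13.1%.

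**The case against.** **Stable patients.** It is tempting to infer that scan error in stable patients would probably produce two responses in Part 1. Five patients in 30 at a true −20%, with 10% CV, give two or more false PRs with probability 56% (8% if two consecutive scans are needed). That case is close to the −30% threshold, where misclassification is greatest, and nothing in the documents supports that mix. Five patients at −10% give 7%, and five with no change give 0.2%. At 5% CV even five at −20% give only 4.6%. This objection stands: the direction of the bias is certain, its size is not.

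**Opening Part 2.** A reader might infer that two responses open Part 2 outright. Protocol 3.1.2 does not say so: two responses allow a substantial amendment to be submitted, with data from ANV419-001 as well, and it must then be approved. Only SAP 2.2.1.2 starts Part 2 on the count alone.

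**Final decision.** The 95% CI rule is strict enough to absorb much of the error. At a true ORR of 20% its pass probability is still 9.5% with 8% false PRs, below the planned 10%. Stage 1 is a futility screen, so a false PR there costs further enrolment but does not make an efficacy claim. Both points stand. They leave the Part 2 trigger and Stage 1 unprotected.

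**Phase 1 comparison.** Protocol 1.3.4 calls the one PR in ANV419-001 confirmed. One might infer that the present ORR is looser than the Phase 1 measure. The text does not say that the earlier ORR required confirmation, so this is not established.

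**Reference to RECIST.** The endpoint is stated as defined by RECIST v1.1. That does not supply a confirmation step, because the rules written out in Appendix C and the SAP contain none.

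**Conclusion.** The point holds as a weakness in the design as written. Primary ORR accepts one local, open-label reading and compares it with fixed rates, so false responses can only raise it. The size is conditional: negligible at 5% CV with a true change of 0 to −10%, and material at 10% to 15% CV or where patients have shrinkage near the threshold. Exposure is greatest at the two-response trigger and at Stage 1, and smaller at the final Part 3 rule.

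The documents do not support reading this as a flaw that affected the trial's outcome. SAP section 5 reports 0 responses in Part 1 and the trial stopped, so confirmed and unconfirmed ORR are both 0 and no decision changed. The change is worth making because it is inexpensive.

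**What to change.** - In Protocol 8.2.4 and Appendix C, and SAP 3.4.1 and 3.4.2.1, define primary ORR as CR or PR confirmed at the next scheduled assessment, with a stated minimum interval. Classify a single-scan response that is not confirmed as SD, and report unconfirmed ORR as a sensitivity analysis.
- Apply the Part 1 and Part 3 counts to confirmed responses.
- Amend Protocol 8.2.3 and SAP section 4 so that Stage 1 is read only after any initial response has had its confirmatory scan.
- State that 6%, 10%, 20% and 40% are confirmed rates, and restate them if they were set on an unconfirmed scale.
- Align SAP 2.2.1.2 with Protocol 3.1.2 on what two responses lead to.

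If unconfirmed ORR was intended, both documents should say so and justify the fixed rates on that basis.

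Cost: a slightly lower ORR and an interim later by about one scan interval. No extra scan is needed if the next scheduled one meets the minimum interval; the schedule is blacked out, so this has to be checked.
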